2. OBJECTIVES AND ENDPOINTS

Objectives	Endpoints
Primary	
To evaluate the efficacy of vutrisiran compared to placebo on reducing all-cause mortality and CV events	 Composite outcome of all-cause mortality and recurrent CV events (CV hospitalizations and urgent heart failure [HF] visits) in the overall population Composite outcome of all-cause mortality and recurrent CV events (CV hospitalizations and urgent HF visits) in the vutrisiran monotherapy subgroup (defined as the group of patients not on tafamidis at study baseline)
Secondary	
To evaluate the efficacy of vutrisiran compared with placebo treatment on: • Functional capacity • Patient-reported health status and health-related quality of life • All-cause mortality • Severity of clinical heart failure symptoms	The following secondary endpoints will be defined in both the overall population and the vutrisiran monotherapy subgroup: Change from baseline in 6-MWT Change from baseline in the KCCQ-OS All-cause mortality Change from baseline in NYHA Class
Exploratory	

Objectives	Endpoints
	• CCI
Pharmacodynamics and Pharmacokinetics	
To characterize the PD effect of vutrisiran on TTR	Change from baseline in serum TTR levels
To characterize plasma PK of vutrisiran	Plasma PK exposure parameters
To assess presence of antidrug antibodies (ADA) against vutrisiran	Frequency and titers of ADA
Safety	
To evaluate the safety and tolerability of vutrisiran in patients with ATTR amyloidosis with cardiomyopathy	Frequency of AEs

3. INVESTIGATIONAL PLAN

3.1. Summary of Study Design

This is a Phase 3, randomized (1:1), double-blind, placebo-controlled, multicenter study to evaluate the efficacy and safety of vutrisiran in approximately 600 patients with ATTR amyloidosis (hATTR or wtATTR) with cardiomyopathy. Approximately 20% of the study population is anticipated to have hATTR and 80% wtATTR amyloidosis with cardiomyopathy.

At baseline, patients are either:

- Tafamidis-naïve (see inclusion criterion #4 for definition); or
- Currently receiving tafamidis (Note: must be on-label use of commercial tafamidis per an approved cardiomyopathy indication in the country of use).

The study consists of 4 periods (Figure 1):

1. **Screening Period:** Up to 45 days during which patients will undergo screening assessments to determine eligibility.

2. Double-Blind (DB) Period:

- At the start of the DB Period (on Day 1), eligible patients will be randomized in a 1:1 ratio to receive blinded doses of 25 mg of vutrisiran or placebo administered as a SC injection q3M (every 12 weeks ±7 days) for up to 36 months.
 - In addition to study drug, all patients will take the recommended daily allowance of vitamin A during their DB Period and Follow-up Period (see below).
- Patients will undergo assessments as outlined in the Schedule of Assessments (Table 1).
- An individual patient's DB Period visits will end after they complete their Month 36 visit, or 30 months after the last patient is randomized, whichever comes first. As such, a patient's last visit during the DB Period may vary from 30 to 36 months after enrollment.
 - The variable length of the DB Period will mean that some patients will not have a Month 33 and/or Month 36 visit. For patients whose last visit in the DB Period was Month 30 (Week 132), Day 1 in the OLE Period will occur 144 weeks (±7 days) after enrollment in the DB Period. For patients whose last visit in the DB Period was Month 33 (Week 144), Day 1 in the OLE Period will occur 156 weeks (±7 days) after enrollment in the DB Period. For patients whose last visit in the DB Period was Month 36 (Week 156), Day 1 in the OLE Period will occur on the same day (since study drug is not administered as part of the Month 36 DB visit).
 - The period of DB exposure, defined as the duration prior to first exposure to open-label treatment, will be 144 to 156 weeks (33 to 36 months).
- The primary analysis will be conducted after the last patient has completed the period of DB exposure or otherwise discontinued.

3. Open-Label Treatment Extension (OLE) Period

The study has been amended (Amendment 4) to include an OLE Period in lieu of the Open-Label Randomized Treatment Extension Period (previously introduced with Amendment 3). In the OLE Period, all patients will receive the vutrisiran 25 mg q3M regimen.

- Upon entry into the OLE, all eligible patients will transition to receive open-label doses of 25 mg q3M vutrisiran administered as SC injections.
- Patients initially randomized to CCI (under Amendment 3) will transition to receive open-label doses of 25 mg q3M vutrisiran administered as SC injections at their next scheduled dosing visit (24 weeks after their last dose of vutrisiran). Patients initially randomized to 25 mg q3M vutrisiran (under Amendment 3) will continue with the 25 mg q3M regimen.
 - In addition to study drug, all patients will take the recommended daily allowance of vitamin A during their OLE Period and Follow-up Period (see below).
- All patients will undergo assessments as outlined in the Schedule of Assessments for the OLE Period (Table 2).

Note: Patients who do not complete the DB Period may not participate in the OLE Period. Consent must be signed before any procedures are performed in the OLE Period (Table 2).

4. Follow-Up Period after the last dose of vutrisiran on study:

- Following completion of the OLE Period (or completion of the DB Period for patients who do not continue into the OLE Period; or their last dose of vutrisiran for patients who discontinue study drug early), patients will commence follow-up visits every 12 weeks for the durations outlined below.
- Prior to unblinding of their treatment from the DB Period, the duration of the Follow-up Period for a patient will be 1 year from their last dose of study drug. For women of child-bearing potential, the duration of the Follow-up Period will be 18 months from their last dose of study drug. Patients will continue vitamin A supplementation during their Follow-up Period.
- After unblinding, all patients who were on placebo, and patients who received vutrisiran whose serum TTR level has returned to ≥80% of baseline or who have completed the Follow-up Period, whichever comes first, may discontinue further follow-up and stop taking vitamin A. Baseline is defined as the last value prior to first vutrisiran dose (ie, prior to the first DB dose for vutrisiran patients in DB Period and prior to the first OLE dose for placebo patients). Patients will be followed for a minimum period as listed below during the Follow-up Period based on treatment regimen received:
 - All patients whose last dose of study drug was 25 mg vutrisiran/placebo during DB Period or 25 mg vutrisiran during the OLE Period will be followed for a minimum of 90 days after their last dose of study drug.

- Patients whose last dose of study drug was Amendment 3) will be followed for a minimum of study drug during Follow-up Period.
- For any patient who starts a TTR lowering treatment as part of clinical care, and has completed a minimum of 90 or (depending on vutrisiran treatment regimen) of safety follow-up since their last dose of study drug, further follow-up will be discontinued.
- Patients will undergo assessments as outlined in the Schedule of Assessments (Table 1 and Table 2).

Patients may receive vutrisiran on the study until the end of the OLE Period or until one of the following occurs: 1) they meet any of the study discontinuation criteria; 2) vutrisiran is commercially available in the patient's country of residence and vutrisiran is accessible to the patient and the patient has completed their OLE Month 12 Visit; or 3) the vutrisiran development program is discontinued.

Study drug dosing may be allowed outside of the study center (eg, the patient's home) during the DB Period or OLE Period under certain circumstances as specified in Section 5.2.2. In addition, routine assessments and collection of relevant safety information may be collected outside the study center as specified in Section 6.

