1.4. Clinical Development of Vutrisiran

Vutrisiran was initially evaluated in a completed Phase 1 study (ALN-TTRSC02-001) in healthy patients, and is currently being investigated in an ongoing Phase 3 study (ALN-TTRSC02-002 [HELIOS-A]) in patients with hATTR amyloidosis with polyneuropathy as described below.

Study ALN-TTRSC02-001 was a Phase 1, randomized, single-blind, placebo-controlled, single-ascending dose study evaluating the safety, tolerability, pharmacokinetics (PK), and pharmacodynamics (PD) of vutrisiran in 80 healthy subjects; 60 subjects received single-doses of vutrisiran (from 5 mg to 300 mg) and 20 subjects received placebo.

Overall, vutrisiran was well tolerated. There were no serious or severe adverse events (AEs) and no subject discontinued from the study due to an AE. Mostly mild, transient, dose-dependent increases in alanine aminotransferase (ALT) and aspartate aminotransferase (AST) were observed in all vutrisiran dose groups, particularly at doses >100 mg. Two subjects had transient, asymptomatic elevations in ALT and/or AST of >3 × the upper limit of normal (ULN). None of the ALT or AST elevations were reported as AEs and none were associated with concurrent bilirubin elevations.

Single SC doses of 25 to 300 mg vutrisiran resulted in robust, and durable reductions in serum TTR protein, with the magnitude and duration of TTR reduction being dose-dependent. At the proposed dose of 25 mg vutrisiran, a single dose resulted in mean maximum TTR reduction of 83%; the nadir was reached at approximately 6 weeks and maintained for 90 days. Based on the results of the Phase 1 Study ALN-TTRSC02-001, vutrisiran 25 mg SC administered once q3M was selected for further development (see Section 1.6 for dose rationale).

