In addition to achieving the same cumulative annual dose of 100 mg as tested in the treatment period in HELIOS-A, observed data from the single-dose Phase 1 study (ALN-TTRSC02-001) and PK/PD modeling show that the column and 25 mg q3M regimens of vutrisiran are expected to achieve comparable average TTR reductions (see Table 9).

- The CCI regimen is expected to achieve slightly higher median peak lowering with lower variability compared with the 25 mg q3M regimen (89.3 % vs 87.8%).
- The 25 mg q3M and CCI regimens are predicted to achieve median trough TTR reduction of 86.4% and 82.5% which are similar to the observed median trough TTR reductions of 81.2% for patisiran at Month 18 of the APOLLO study. [Adams 2018]
- Importantly, the steady state average TTR lowering of both 25 mg q3M and CCI are expected to be similar (87.1% vs 86.7%).

The TTR lowering expected with 25 mg q3M or CCI dosing regimens of vutrisiran is similar to that observed with patisiran in APOLLO, and hence is expected to translate into similar clinical efficacy.

Table 9:	Summary of Observed and Predicted Median TTR Reductions (%) for
	25 mg q3M Vutrisiran, and 0.3 mg/kg q3W Patisiran Regimens

	Vutrisiran (Model-predicted)		HELIOS-A Vutrisiran (Observed)	APOLLO Patisiran ^c (Observed)
Serum TTR % change from baseline	25 mg q3Ma	CCI	25 mg q3M	0.3 mg/kg q3W
Peak	-87.8 (-97.8, -51.7)	-89.3 (-97.9, -57.0)	-90.8 ^d (-97.7, -63.4)	-88.5 (-95.4, -56.8)
Trough	-86.4 (-97.7, -43.7)	-82.5 (-97.5, -31.4)	-86.2° (-97.3, -41.8)	-81.2 (-94.2, -49.9)
Average	-87.1 (-97.7, -48.6)	-86.7 (-97.7, -46.9)	-86.9 ^f (-97.5, -42.1)	-83.1 (-93.7, -56.5)

Abbreviations: q3M=once every 3 months; CCl; q3W=once every 3 weeks;

The numbers in table are median and 5th and 95th percentiles of simulations (vutrisiran) or observed data (patisiran)

Importantly, the available safety data in healthy volunteers, as well as exposure-response modeling, suggest the two regimens will result in similar safety profiles. In the Phase 1 study, vutrisiran demonstrated an acceptable safety profile at single doses up to 300 mg. The data to date in HELIOS-A also support that vutrisiran continues to have an acceptable safety profile.

In summary, the adjustment of the study design to include an RTE Period will facilitate a descriptive comparison of safety, PD, PK, and efficacy of the comparison of safety, PD, PK, and efficacy of the regimen relative to the 25 mg q3M dose regimen. The comparable to the 25 mg q3M regimen.

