Following appropriate training on study drug administration, dosing may be permitted by the patient or caregiver at all dosing timepoints under the oversight of the Investigator and following consultation with the Medical Monitor. This measure is intended to remain in effect only during periods of time when the COVID-19 pandemic impedes the ability of patients to travel to the study site or healthcare professionals to go to patients' homes for dosing. In addition, added references to patient/caregiver instructions for administration, storage of study drug, and reporting of product complaints.

• Expanded Dosing Window After Which a Dose Will be Considered Delayed

If a patient does not receive a dose of study drug within the specified dosing window, the dose may be administered with up to an 8-week delay (previously 6 weeks) to be considered a delayed dose. If the delay in dose is related to COVID-19, the Medical Monitor should be informed of any delayed doses (previously consultation with the Medical Monitor was required prior to administration of the delayed dose).

This change has been implemented to provide greater flexibility amid travel and other restrictions related to the COVID 19 pandemic, in order to minimize the number of missed doses on study. Given the long activity of vutrisiran resulting in sustained suppression of TTR as observed in Phase 1 study, an occasional delay of 8 weeks in dosing is expected to have minimal impact on the TTR suppression (decrease of only 7% in TTR suppression relative to vutrisiran original scheduled dosing) as predicted by the Sponsor's PK/PD modeling. Resumption of dosing as per the original dosing schedule is expected to be tolerated based on the safety data from the Phase 1 study which evaluated, and demonstrated an acceptable safety profile, at doses as high as 300 mg (12× higher than the therapeutic dose of 25 mg administered quarterly).

• Screening Patients

The requirement that the Investigator notify the Sponsor before screening patients was added to allow an assessment of the ability of the study center or any new trial participant to comply with the protocol given the COVID-19 limitations.

In addition, patients who failed screening due to situations related to the COVID-19 pandemic may be allowed to rescreen after consultation with the Medical Monitor.

• Assessments Performed Outside the Study Center

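### The post-unblinding release of placebo patients from follow-up and vitamin A does not exclude those who crossed over to vutrisiran in the OLE

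*Protocol*

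**What the plan says.** The rule is in Protocol 3.1, under the Follow-Up Period, and is repeated in the Synopsis. Before unblinding, follow-up lasts 1 year from the last dose (18 months for women of child-bearing potential), with vitamin A throughout. The groups allowed to stop both early are then given as "After unblinding, all patients who were on placebo, and patients who received vutrisiran whose serum TTR level has returned to ≥80% of baseline". For vutrisiran patients, finishing the Follow-up Period is the alternative, and the sooner of the two counts.

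Three neighbouring statements bear on it:

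- The sentence directly after defines the TTR baseline. For those randomized to placebo it is the last value "prior to the first OLE dose for placebo patients".
- A patient whose last dose was 25 mg vutrisiran in the OLE "will be followed for a minimum of 90 days after their last dose of study drug".
- On the extension, the same section states: "In the OLE Period, all patients will receive the vutrisiran 25 mg q3M regimen".

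**The concern.** A patient randomized to placebo who enters the OLE meets both descriptions in the release rule: placebo in the double-blind period, and vutrisiran received. The placebo description comes with no TTR condition. The rule grants permission to each group, so meeting the second description does not withdraw what the first allows.

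The baseline sentence points the other way. It uses the placebo label for people who go on to an OLE dose and gives them a TTR reference value. So the label includes crossed-over patients in one sentence and, for the rule to work, must exclude them in the sentence before.

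At stake is the length of safety follow-up and vitamin A supplementation for patients whose TTR is still suppressed. A second effect is uneven practice: about 150 centers apply the rule patient by patient. This is also an ordinary route through the trial. Unblinding follows database lock for the primary analysis (Protocol 3.6), and the data cutoff is set at about the time the last patient enters the OLE (SAP 4.2). The OLE lasts up to 24 months, so many crossed-over patients can be expected to reach follow-up after unblinding.

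**Working it through.** The plan gives no figure of its own on this point. The check compares the texts and then sizes the gap between the two readings.

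**1. Is the placebo clause narrowed anywhere?** No limit to patients who never received vutrisiran was found in the current text of either document. SAP 3 does name the group that took placebo first and switched in the OLE, when it defines the All Vutrisiran Treated Set. That shows the group was recognized; it does not govern the release rule.

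**2. Duration at issue.** Inputs: 90-day minimum, 1-year and 18-month follow-up (Protocol 3.1), and the SAP's month of 30.4375 days (SAP 5.5).

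- Most patients: 365 − 90 = 275 days.
- Women of child-bearing potential: 18 × 30.4375 = 548 days; 548 − 90 = 458 days.
- 12-weekly visits counted from the last dose and falling after day 90: days 168, 252 and 336 (3 visits by day 365), plus 420 and 504 (5 visits by day 548).

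These are ceilings. The gap is shorter if TTR recovers to 80% sooner.

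**3. Where TTR stands near day 90.** Residual TTR = 100% − reduction.

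| Source | Time after dose | Reduction | TTR, % of baseline |
|---|---|---|---|
| Phase 1, one 25 mg dose, healthy subjects (Protocol 1.4) | to 90 days | mean maximum 83% | 100 − 83 = 17 |
| Sponsor's model, 25 mg q3M trough (Protocol 10.4.3, Table 9) | 12 weeks | median 86.4% | 100 − 86.4 = 13.6 |
| Same, 5th and 95th percentiles | 12 weeks | 97.7% and 43.7% | 2.3 and 56.3 |
| Polyneuropathy trial, observed trough (Table 9) | 12 weeks | median 86.2% | 100 − 86.2 = 13.8 |
| Same, upper limit | 12 weeks | 41.8% | 100 − 41.8 = 58.2 |

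For the single dose, Protocol 1.4 reports that "the nadir was reached at approximately 6 weeks and maintained for 90 days". The q3M trough at day 84 comes six days before the 90-day minimum. Every value in the table is below 80%, including the upper limits.

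**4. A later point.** For an 8-week dosing delay (12 + 8 = 20 weeks, day 140), Protocol 10.4.5 predicts a "decrease of only 7% in TTR suppression relative to vutrisiran original scheduled dosing". If this refers to the value just before the delayed dose:

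- As percentage points: 100 − (86.4 − 7) = 20.6% of baseline.
- As a relative change: 100 − 86.4 × 0.93 = 19.6% of baseline.

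If it is an average over the interval, the day-140 value would be higher. This is supporting evidence only.

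**5. Number of patients.** The planned placebo arm is 600 / 2 = 300, an upper bound. An affected patient must have entered the OLE, be in follow-up after unblinding, have TTR still below 80%, and not have started TTR-lowering treatment in clinical care. The documents give no count.

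**The case against.** The best reply is that there is no true contradiction. On the literal reading the baseline sentence is merely redundant. A reading that gives effect to both sentences is also available: crossed-over patients received vutrisiran, have a pre-OLE baseline, and so follow the TTR rule. A careful investigator would probably apply it that way. This has force and is why the point is minor. But a reading that can be inferred is not an instruction.

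The documents also support 90 days after 25 mg in other places: as the minimum safety follow-up, as the breastfeeding advice in 6.5.6.7, and in the abstinence provision of 5.6.1. Protocol 1.7 says that the fall in circulating vitamin A does not lead to severe deficiency. Release is permitted, not required, and a patient who starts TTR-lowering treatment in clinical care leaves after the minimum in any case. All of this stands and limits the harm. It does not make the 90-day floor a substitute for the TTR rule, because TTR near day 90 is far below the protocol's own threshold.

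An effect on contraception and pregnancy reporting is doubtful. Both run to the end of the Follow-up Period, and the release sentence itself separates completing that period from stopping early. The 458-day figure would apply to few patients: about 80% of the trial is expected to have wild-type disease, which the protocol describes as typical after age 70 and mainly in men.

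Lastly, the durations are ceilings, and the TTR data come from healthy subjects and polyneuropathy patients. They support TTR below 80% near day 90; they do not show how long it stays there.

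**Conclusion.** The concern holds, at the lowest level of importance. As written, the placebo clause releases crossed-over patients without a TTR condition, while the next sentence implies that they were meant to have one. Taken literally, the rule lets such a patient stop safety follow-up and vitamin A 90 days after the last vutrisiran dose, with TTR probably near 14% to 17% of baseline. That is up to 275 days before the end of full follow-up, or up to 458 days for the few women of child-bearing potential.

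The TTR figures assume that Phase 1 and polyneuropathy data carry over to this population. The number affected is unknown and is smaller than the planned placebo arm of 300.

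The efficacy analyses, type I error and power are untouched. So are the windowed adverse event summaries, whose windows of 84 days (SAP 5.11.1) and 83 days (SAP 6.1) close before day 90.

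**What to change.** Change two phrases, in Protocol 3.1 and in the Synopsis:

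- Limit the unconditional release to *patients who received only placebo and no vutrisiran in the study*.
- Apply the TTR condition to *patients who received vutrisiran in the DB or OLE Period*.

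Crossed-over patients then follow the TTR rule with the baseline already defined for them. The wording also covers a placebo-randomized patient given vutrisiran in error, a case that SAP 3 and 5.8 foresee.

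The cost is an administrative letter or a line in the next amendment. No assessment is added, since TTR is already scheduled at follow-up visits in Protocol Tables 1 and 2. Some crossed-over patients would stay in follow-up longer than under the literal reading, as the rule seems to have intended.

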3.2. Duration of Treatment

The planned duration of treatment for each patient is up to approximately 60 months (approximately 5 years), inclusive of the 33 to 36-month DB Period and a 24-month OLE Period.

3.3. Duration of Study Participation

The estimated total time on study for each patient is up to approximately 6 years, including a Screening Period of up to 45 days, a DB Period of up to 36 months, an OLE Period of up to 24 months, and a Follow-up Period of up to 1 year after the last dose of study drug (18 months for women of child-bearing potential).

3.3.1. Definition of End of Study for an Individual Patient

A patient is considered to have reached the end of the study if they have:

- completed the DB Period and the Follow-up Period (if the patient does not continue into the OLE Period);
- completed the DB Period, the OLE Period, and the Follow-up Period;
- completed the Early Study Discontinuation Visit; or
- started a TTR-lowering regimen as a part of clinical care

